5.3.1 Breaking of blinding

The PI, [name], is not blinded in this study. [name] and her laboratory team will be blinded to the intervention. It is not likely that a need for unblinding of the laboratory team will be needed however in such extreme circumstance (e.g. unusual and severe infection in which detailed knowledge of bacterial species in the wound may expedite administration of life saving antibiotic therapy) at his discretion the PI may decide to break blinding. This will be documented and considered in the data analysis.

5.4 Informed consent

On visit S1 each subject will be given an informed consent form (ICF) and ample time to review the information. All questions will be answered by study staff. As detailed in section 8.2 no study procedure should commence prior to ICF signature and subject expression of clear understanding of study procedures.

5.5 Eligibility

Prior to randomization the PI and study staff will ensure subject met all inclusion and exclusion criteria. If all criteria are met, subject will be deemed eligible for participation and proceed to randomization.

5.6 Demographics

Basic demographic data on each subject will be collected at the S1 visit.

5.6.1 Demographic data

The following demographic data to be collected:

- a. Name
- b. Date of birth
- c. Contact information (address, email address, telephone numbers)
- d. Gender
- e. Race
- f. Ethnicity
- g. History and current tobacco products use (pack years)
- h. Height (in meters)
- i. Body weight (in kilograms)

5.7 Quality of life assessments

The EQ-5D-5L and the WQoL instruments will be used and assessments take place at visits T1, F1 and F2. The EQ-5D-5L consists of 2 pages – the EQ-5D-5L descriptive system (page 2) and the EQ Visual Analogue scale (EQ VAS) (page 3). The descriptive system is comprised 5 dimensions: mobility, self-care, usual activities, pain/discomfort, anxiety/depression. Each dimension has 5 levels: no problems, slight problems, moderate problems, severe problems, and extreme problems. The subjects will be asked to indicate his/her health state by checking in the box against the most appropriate statement in each of the 5 dimensions. The EQ VAS records the respondent's self-rated health on a 20 cm vertical, visual analogue scale with endpoints labelled 'the best health you can imagine' and 'the worst health you can imagine'. This information can be used as a quantitative

measure of health as judged by the individual respondents. The instruments and detailed instructions are presented in appendix 9.8.

The WQoL instrument was developed specifically to address health related quality of life outcomes in people with wounds [24]. The WQoL is a short questionnaire measuring health-related quality of life (HRQoL) in chronic wounds and is composed of seventeen items attributed to three subscales on everyday life, body, and psyche.

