6.1 Schedule of assessments

- 6.2 Handling of unscheduled visits
- 6.3 Handling of missed visits
- 6.4 Stopping rule
- 7. Statistical methods
- 8. Regulatory and ethical issues
 - 8.1 Protocol institutional approval
 - 8.2 Informed consent
 - 8.3 Data handling, safety and quality assurance
 - 8.3.1 Source documentation
 - 8.3.2 Data safety
 - 8.3.3 Data quality assurance
 - 8.4 Good clinical practice
 - 8.5 Study duration and premature termination
- 9. Appendices
 - 9.1 Appendix A – Molecular microbiological protocol
 - 9.2 Appendix B – Application of Comprifore system
 - 9.3 Appendix C – Ankle brachial index measurement
 - 9.4 Appendix D – Itch assessments
 - 9.5 Appendix E – Insight wound imaging system
 - 9.6 Appendix F - Acticoat 7® application instructions
 - 9.7 Appendix G - Wound-QoL questionnaire
 - 9.8 Appendix H - EQ-5D-5L instrument
- 10. References

1. EXECUTIVE SUMMARY:

Sponsor: BSN Medical Inc.

Primary investigators:

[name], MAS. Assistant professor of dermatology, University of Miami, FL

[name]. Assistant professor of dermatology, University of Miami, FL

[name]. Associate Professor of Biostatistics, University of Miami, FL

Objective: The goal of the study is to investigate the effectiveness of Cutimed® Sorbact® (Study Device) in modifying bacterial load in venous leg ulcers (VLU).

Design: This is an exploratory study in a single center, observer masked, active control, randomized trial.

Overall, 45 subjects with VLU who have persistent wounds and have been previously treated with silver based therapy will be 1:1 randomized to receive up to four applications over up to four weeks of Study Device or Comparator (silver impregnated contact layer dressing - Acticoat®) with 2 weeks follow up period.

Outcomes: Primary outcome is the change in bacterial load compared to baseline.

Secondary outcomes: Bacterial silver resistance based on genetic and phenotypic characterization over time (see appendix A for molecular microbiology protocol), healing rate, complete healing at 6 weeks, pain, quality of life (QOL) measurements and adverse events.

1.1 Table of assessments and study calendar:

Phase	Screening		Treatment					Follow up	
	-2	-1	0		+1	+2	+3	+4	
Week	S1	S2	T0 (pre random)	T0(post random)	T1	T2	T3	T4	F1
Visit		±2	±2		±2	±2	±2	±2	±2
Window (days)									
Informed consent	X								
Eligibility	X	X	X						
Demographics	X								
Medical history	X								
Concomitant medication	X	X	X		X	X	X	X	X
Study ulcer history									

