Physical exam (focused)	X								X
Vital signs	X								X
Pain (VAS)	X	X	X		X	X	X	X	X
Wound area	X	X	X		X	X	X	X	X
Product application				X	X	X	X		
Tissue collection			X			X	X		
QOL				X				X	X
Randomization				X					
Sharp debridement	X	X		X	X	X	X	X	
Wound photography	X	X		X	X	X	X	X	X
Compression	X	X		X	X	X	X	X	X
Adverse events	X	X	X		X	X	X	X	X
ABI	X								
Venous Doppler	X								
Fitting for stocking								X	X

Table 1. Table of assessments and study calendar

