3. STUDY DESIGN

3.1 Overview:

This is an exploratory, single center, observer masked, active control, 1:1 randomized clinical trial. The goal is to compare the effectiveness of Study Device (Cutimed® Sorbact® wound contact layer) to an active control (silver contact layer Acticoat®). Both devices are already approved and indicated for treatment of wounds. Standard care selected for use in this trial includes sharp debridement and compression with Jobst Comprifore® 4 layer compression system.

The study consists of three phases: two weeks screening phase (phase-1), up to four weeks treatment phase (phase-2), and two weeks follow up phase (phase-3).

In the screening phase i.e. phase-1, the Investigators will choose Study Ulcer, make baseline measurements and assessments and verify inclusion and exclusion criteria are met. Standard care will be applied without use of Study Device or active control.

The treatment phase i.e. phase-2 may last up to four weeks (if healing did not occur prior) and includes application of study dressings as well as application of standard care and measurements of primary and secondary outcomes. This will be achieved by tissue collection procedures conducted at visits T0, T2, and T3. [name] and her research team will conduct the molecular microbiology and standard microbiology assessments of the specimens collected in this study. Gene expression (by qPCR) and standard microbiology will be utilized to characterize the mechanisms through which Cutimed® Sorbact® changes the bacterial load and promotes healing of chronic venous leg ulcers. Understanding the mechanism through which Cutimed® Sorbact® stimulates healing in patients may promote, improve and expand its clinical use.

In the two weeks follow up phase i.e. phase-3 subjects will return for one visit and secondary outcomes will be assessed and standard care provided. The subjects will then be discharged from the study and return to their wound care provider for further management as indicated.

3.2 Study outcomes:

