3.2.2 Secondary outcomes

Secondary outcomes will include:

Microbiological outcomes: bacterial silver resistance characterization on molecular and phenotypic level over time (see appendix A for molecular microbiology protocol).

Clinical wound outcomes: healing rate and percent reduction in area over 6 weeks will be calculated by measuring wound area at each visit and dividing the area change by 6 to calculate average wound healing rate in cm^2/week and the average percent reduction for each study arm.

Complete healing at 6 weeks – the proportion of subjects in each study arm in which the study ulcer achieved complete healing at visit F1.

Pain related outcomes: pain assessments will be collected at every visit using visual analog scale (VAS) and time from visit T0 to clinically meaningful decrease in pain (i.e. 33% reduction from baseline) [21] will be calculated. Additionally, time to first indication of no pain will be calculated (i.e. VAS < 5mm)

Quality of life measurements: the EQ-5D-5L [22] and the Wound Quality of Life (WQoL) [23, 24] instruments will be used and assessments take place at visits T0, T4 and F1.

Safety outcomes: adverse events will be recorded at every visit and type and frequency logged and compared between arms.

4. Study population

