6.1 Schedule of assessments

Assessments will be conducted as described in the protocol according to the schedule presented in Table 1.

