9.1 Appendix A - Molecular Microbiology Protocol ([name])

PURPOSE

The purpose of this protocol is to describe the methods that will be used to evaluate modifying bacterial load and silver resistance in samples from venous leg ulcers (VLU) subjects who have undergone standard of care treatment with Study Device (Cutimed® Sorbact®) and standard of care treatment with active control (Acticoat®) over a 4-week period. Genetic analyses (by qPCR) and standard microbiology will be utilized to characterize the mechanisms through which Cutimed® Sorbact® modifies bacterial load and promotes healing of chronic VLU. Understanding the mechanism through which Cutimed® Sorbact® stimulates healing in patients may promote, improve and expand its clinical use.

INTRODUCTION

The goal of the study will be to investigate the effect and mechanism of action of Cutimed® Sorbact® on bacterial populations and their silver resistance in VLU. Cutimed® Sorbact® products are BSN's proprietary technology dressing device for treating VLU.

Background and Rationale: Our previous *in vivo* studies utilizing porcine wound model have shown that silver treatment induces expression of virulence genes important for biofilm formation in clinical isolates of methicillin resistant *Staphylococcus aureus* and *Acinetobacter baumannii* [15]. Furthermore incidence of silver resistance is an emerging problem in treatment of chronic wound pathogens , [12].

Design: The study is multicomponent involving a clinical study guided by [name] and molecular laboratory component by [name].

The clinical study will enroll 30 patients with VLU who have been exposed to silver based therapy. Following a 2-week run-in phase, 15 subjects will be receiving Cutimed® Sorbact®, while other 15 subjects will receive common wound care product containing silver, Acticoat® in addition to standard of care (SOC). The treatment phase will last 4 weeks followed by a follow up visit 2 weeks later. The standard care involves weekly visits in which wounds will be cleaned and debrided. Debridement tissue from the wounds will be collected for molecular microbiological investigation.

Location: Subjects will be provided standard care at the UM dermatology clinical trials unit. The clinical team led by [name] is pursuing UM IRB approval. [name] and her team will conduct the molecular microbiology and standard microbiology assessments of the specimens collected in this exploratory patient outcome study.

RATIONALE

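### Section 5.7 lists quality-of-life visits (T1, F1, F2) that conflict with 3.2.2 and Table 1 (T0, T4, F1), and F2 is not a defined visit

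*Combined protocol and SAP*

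**What the plan says.** Quality of life is a listed secondary outcome, measured with the EQ-5D-5L and the Wound-QoL. Three places in the protocol say when.

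- Section 3.2.2 (Secondary outcomes): "assessments take place at visits T0, T4 and F1".
- Table 1 (section 1.1), QOL row: marks under T0 (post random), T4 and F1.
- Section 5.7 (Quality of life assessments): "assessments take place at visits T1, F1 and F2".

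On follow-up visits, section 3.1 states "In the two weeks follow up phase i.e. phase-3 subjects will return for one visit", and Appendix A states "The treatment phase will last 4 weeks followed by a follow up visit 2 weeks later". The last column of Table 1 is F1.

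Section 6.1 says that assessments are carried out as the protocol describes them and "according to the schedule presented in Table 1". Section 7 says that the secondary endpoints, quality of life among them, are to be handled with methods like those for the primary endpoint. For the primary endpoint these are a comparison of change from T0 between arms and a repeated measures regression.

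**The concern.** Section 5.7 tells staff how the questionnaires are given, and the visits it names differ from those in the outcome definition and the study calendar. One of its visits does not exist. Another, T1, comes after randomised treatment has begun.

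What is at stake is the baseline. A questionnaire not given before treatment cannot be recovered later. Without it there is no change score and no baseline adjustment. With about 15 subjects per arm (section 4.1), chance differences between arms at baseline can be sizeable. Section 7 also says that the study is meant to supply effect estimates for sizing later trials, so losing the baseline would weaken what the pilot can deliver on this outcome.

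**Working it through.** No figure in the plan has to be reproduced. The check sets the visit lists side by side.

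**Reading Table 1.** The visit columns, in order, are S1, S2, T0 (pre random), T0 (post random), T1, T2, T3, T4 and F1, nine in all. The QOL marks fall in columns 4, 8 and 9. Two other rows confirm this reading. The Randomization mark falls in column 4. The Product application marks fall in columns 4 to 7, which makes four and agrees with the maximum of four applications in section 1.

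| Visit | Timing | 3.2.2 | Table 1 | 5.7 |
|---|---|---|---|---|
| T0 | week 0 | yes | yes (post-random column) | no |
| T1 | week +1 | no | no | yes |
| T4 | week +4 | yes | yes | no |
| F1 | 2 weeks after the treatment phase | yes | yes | yes |
| F2 | not defined | no | no | yes |

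**Overlap.** {T0, T4, F1} and {T1, F1, F2} share only F1, which is 1 of 3 visits. Following 5.7 to the letter would omit T0 and T4, so 2 of the 3 planned readings. It would add T1, and F2 cannot be done. The readings actually obtained would be T1 and F1.

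**Can T1 stand in for T0?** The first study dressing goes on at T0, after randomisation, so T1 falls about one week into treatment (each visit has a window of 2 days either way). The Wound-QoL in Appendix G asks about the preceding seven days, which at T1 is essentially the first treated week. The EQ-5D-5L in Appendix H asks about the current day, which is also after treatment has started. Neither gives a pre-treatment value.

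**Can F1 stand in for T4?** The last study dressing goes on at T3, so the seven-day recall at T4 covers the last treated week. F1 comes two weeks after T4, and section 5.15.1 says that neither study product is applied during follow-up. F1 measures a different period.

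**Timing within T0.** Section 3.2.2 says only T0. Table 1 splits T0 in two and puts the questionnaires in the post-random half, the same column as randomisation itself. The order of events within that column is not stated. Section 5.3 describes subject blinding as unlikely, so it matters whether subjects answer before or after they can learn their allocation.

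**The case against.** The strongest reply is that the intended schedule is clear. Section 6.1 names Table 1 as the schedule, and Table 1 agrees with the outcome definition in 3.2.2. Other procedure sections (5.12, 5.13, 5.14, 5.17) defer to the table. The error in 5.7 also partly reveals itself, because anyone trying to book F2 would have to go back to Table 1. The labels may simply be left over from an older scheme. Exclusion criteria 2 and 3 in section 4.3 speak of treatment visit 1 where the baseline visit seems to be meant, so T1, F1 and F2 may once have stood for baseline, end of treatment and follow-up. Finally, this is one of several secondary outcomes in a pilot of 30 with no power calculation.

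Most of this stands. It makes the loss of data conditional, and it keeps the point below anything that touches the primary outcome. It does not remove the conflict. Section 6.1 also refers to assessments as the protocol describes them, 5.7 is where this one is described, and no rule of precedence is given. Unlike the sections that defer to the table, 5.7 names its own visits. The explanation by old labels is an inference, and under the labels that Table 1 now defines, T1 is week +1.

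A reader might infer more than the documents support:

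- *That the trial will have no quality-of-life baseline.* This follows only if 5.7 is followed against both Table 1 and 3.2.2.
- *That T1 is meant to serve as the baseline value.* No section says so.
- *That no quality-of-life comparison would survive.* Even under 5.7, the arms could be compared at T1 and at F1 as randomised groups. It is change from baseline and the end-of-treatment comparison that would be lost.
- *That Table 1 already calls for a questionnaire before randomisation.* It does not, since its mark is in the post-random column. Nor does the mark show that subjects answer after learning their allocation, because the order within the column is open.

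**Conclusion.** Section 5.7 is wrong as written and should be corrected. It agrees with 3.2.2 and Table 1 on one visit of three and names one visit that does not exist. Followed literally, it would leave no pre-treatment and no end-of-treatment reading for a listed secondary outcome.

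How much this matters depends on two things. First, data are lost only if staff take the visits from 5.7 rather than from Table 1. The documents favour Table 1 but do not settle the matter. Second, that change from baseline is the planned quality-of-life analysis is read from section 7, which applies primary-type methods to the secondary endpoints. Section 3.2.2 does not itself define the outcome as a change.

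The position of the T0 questionnaire relative to disclosure of the allocation is a separate and smaller gap. It would remain after 5.7 is brought into line.

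**What to change.** Change the visits in section 5.7 to T0, T4 and F1, so that it matches 3.2.2 and Table 1. This costs one line of text and adds no assessment.

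As a separate change, state in 5.7 that the T0 questionnaires are completed before the allocation is disclosed to the subject, and move the T0 mark in the QOL row of Table 1 from the post-random to the pre-random column. This costs one sentence and one moved mark. The two edits should be made together: a note in 5.7 that the questionnaire comes before randomisation, with Table 1 left as it is, would replace one mismatch with another.

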5.8 Medical history

During the S1 visit pertinent medical history data will be collected from the subjects:

- a. List of active medical conditions
- b. List other non-active (resolved) medical conditions
- c. For each diagnosis the diagnosis name, date of diagnosis and status (i.e. active / non-active) should be listed.
- d. New diagnoses arising during study judged by PI as non adverse events will be recorded in the medical history section. Medical histories items should be categorized as follows:

i. Cardiovascular	viii. Immunologic
ii. Dermatologic	ix. Lymphatic
iii. Endocrine	x. Neurological
iv. Gastrointestinal	xi. Other
v. Genitourinary	xii. Psychiatric
vi. Hematologic	xiii. Renal
vii. Hepatic	xiv. Respiratory

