5.19.2 Definition of an adverse event

In this study an adverse event (AE) will be defined based on FDA CFR Title 21: "Adverse event means any untoward medical occurrence associated with the use of a drug in humans, whether or not considered drug related" [28]. Therefore an AE is considered as any unplanned medical occurrence that affects subject's health and/or well-being. The adverse event need not be directly related to the study device or procedure. As such, an adverse event may include any unintended outcome such as a symptom or a new diagnosis or worsening or improvement of existing medical condition.

Serious adverse event (SAE) is defined according to FDA CFR title 21: "Serious adverse event or serious suspected adverse reaction. An adverse event or suspected adverse reaction is considered "serious" if, in the view of either the investigator or sponsor, it results in any of the following outcomes: Death, a life-threatening adverse event, inpatient hospitalization or prolongation of existing hospitalization, a persistent or significant incapacity or substantial disruption of the ability to conduct normal life functions, or a congenital anomaly/birth defect. Important medical events that may not result in death, be life-threatening, or require hospitalization may be considered serious when, based upon appropriate medical judgment, they may jeopardize the patient or subject and may require medical or surgical intervention to prevent one of the outcomes listed in this definition. Examples of such medical events include allergic bronchospasm requiring intensive treatment in an emergency room or at home, blood dyscrasias or convulsions that do not result in inpatient hospitalization, or the development of drug dependency or drug abuse".

A SAE is therefore an AE that:

1. Results in death.
2. Is life-threatening at the time of the AE.
3. Results in an inpatient hospitalization or prolongation of existing hospitalization.
4. Results in a persistent or significant incapacity or substantial disruption of the ability to conduct normal life functions.

5. Is a congenital anomaly/birth defect.
6. May require medical or surgical intervention to prevent one of the outcomes listed above.

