5.19.3 Documenting and reporting adverse events

All adverse events need to be recorded and reported to the local IRB and the sponsor in a timely manner and in accordance to local regulations.

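### Section 5.8 item d lets the unblinded PI file a diagnosis arising during the study as medical history, without limiting this to conditions that predate consent, and so conflicts with the broad AE definition in 5.19.2

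*Combined protocol and SAP*

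**What the plan says.** Section 5.8 describes the history taken at visit S1. Its item d goes further and covers what happens later: "New diagnoses arising during study judged by PI as non adverse events will be recorded in the medical history section". It gives no onset date, severity threshold or list of conditions to guide that judgement.

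Section 5.19.2 sets the AE definition. Its own summary reads: "Therefore an AE is considered as any unplanned medical occurrence that affects subject's health and/or well-being". It adds: "The adverse event need not be directly related to the study device or procedure". It then gives examples: "an adverse event may include any unintended outcome such as a symptom or a new diagnosis or worsening or improvement of existing medical condition".

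The safety provisions that follow are written for AEs:

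- Section 3.2.2, on safety as a secondary outcome: "adverse events will be recorded at every visit and type and frequency logged and compared between arms".
- Section 5.19.3: "All adverse events need to be recorded and reported to the local IRB and the sponsor".
- Section 5.19.4 has the PI assign a causality category to each AE.

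On masking, section 5.3.1 says the PI "is not blinded in this study". The independent blinded monitor in section 5.3 confirms healing from images and has no role in classifying AEs.

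**The concern.** Two sections govern the same object, a diagnosis that first appears after the subject has joined the study. One treats it as an example of an AE. The other lets the PI decide that it is not one and file it elsewhere. Under 5.19.2, lack of relation to the dressing cannot be the reason for that decision, and 5.8 item d supplies no other reason.

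The decision comes before everything else in the safety plan. A diagnosis not classed as an AE is not counted in the comparison by arm, is not covered by the AE reporting rule and receives no causality category. Because the person deciding knows the allocation, a difference between arms in how readily diagnoses are called AEs could shift the safety comparison in either direction. Section 7 says the pilot is meant to produce effect estimates for planning later studies, so descriptive AE frequencies are among its outputs and should not depend on an undefined filter.

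**Working it through.** The plan gives no AE rate or other figure to reproduce here. The check is a comparison of the sections, followed by a short illustration of scale.

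**Step 1: do the two rules overlap?** Item d applies to diagnoses that arise during the study. Section 5.19.2 covers any unplanned medical occurrence affecting health or well-being and lists a new diagnosis among its examples. A diagnosis with onset after consent that affects health falls under both. They overlap.

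**Step 2: is there a legitimate remainder for item d?** Yes. Section 5.19.2 says an AE *may include* a new diagnosis, not that every new diagnosis is one. A condition present before consent and only discovered during the study can properly be history. Item d is not confined to that case.

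**Step 3: who decides, and who checks?** The PI decides, knowing the allocation (5.3.1). The masked roles in 5.3 are the laboratory and the image reviewer for healing. Neither reviews the AE decision. Section 8.3.3 provides periodic review of all study materials for completeness and accuracy, which reaches medical history entries, but it does not describe a masked or independent ruling on AE status.

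**Step 4: what follows from filing as history?**

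| Provision | Written for | Diagnosis filed as history |
|---|---|---|
| Comparison by arm (3.2.2) | AEs | could be omitted |
| IRB and sponsor reporting (5.19.3) | AEs | could be omitted |
| Causality category (5.19.4) | AEs | could be omitted |
| Source record and monitoring (8.3.1, 8.3.3) | all study materials | retained |

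**Step 5: scale, for illustration only.** Section 4.1 aims for 15 completers per arm. If one subject's only event is filed as history, that arm's proportion with an AE changes by 1/15 = 6.7 percentage points; two subjects give 2/15 = 13.3 points. AEs also occur in subjects who do not complete. On the 35 who may be enrolled under 4.1, an arm averages 35/2 = 17.5 subjects, and one subject is 1/17.5 = 5.7 points.

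Assume, since the plan states no rate, that 6 of 15 in each arm have an AE, and that some subjects in one arm are reclassified:

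| Reclassified | Proportions | Apparent difference | Fisher exact p |
|---|---|---|---|
| 1 | 5/15 vs 6/15 | 6.7 points | 1.00 |
| 2 | 4/15 vs 6/15 | 13.3 points | 0.70 |
| 3 | 3/15 vs 6/15 | 20.0 points | 0.43 |

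On these assumed counts, the descriptive proportions move noticeably while the test stays far from significance. Section 3.2.2 compares type and frequency, so the proportion of subjects is only one of the quantities affected.

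**The case against.** The strongest reply is that the sections can be read in sequence: apply the definition in 5.19.2 first, then use item d to file whatever falls outside it. On that reading the criterion is the AE definition itself, and item d is only a filing instruction. Section 5.19.1 also makes the PI and staff responsible for soliciting and recording AEs and has them ask about health changes at each visit.

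This reply has force, and it limits the point in four ways.

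- A reader might infer that the plan allows a plainly treatment-relevant event, such as leg cellulitis or contact dermatitis newly diagnosed at T2, to be filed as history. It does not. Such events clearly meet 5.19.2, and filing them as history would misapply the protocol.
- A reader might infer that these diagnoses disappear. They remain in the subject's record and open to monitoring review, and section 5.9 requires medication changes to be recorded at every visit, so a treated event would leave a further trace.
- A reader might infer that AE reporting and causality assessment are the only safety oversight. They are not. Section 6.4 allows the PI to stop for safety, 8.1 assigns a regulatory monitor, 8.3.3 provides periodic review, and 8.5.2 covers early termination.
- A reader might infer that bias is demonstrated. The documents show only that the wording leaves room for it.

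The sequential reading still does not settle the matter. If 5.19.2 is applied as broadly as it is written, the clear legitimate use of item d is a condition that predates consent, and item d does not say so. It describes diagnoses arising during the study and leaves their status to an unmasked judgement that no masked or independent person reviews.

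**Conclusion.** The point holds in this limited form. Item d of section 5.8 conflicts as written with the AE definition in 5.19.2, because it lets the unblinded PI treat a diagnosis arising during the study as history without restricting this to pre-consent onset. The consequence is possible omission from the between-arm AE comparison, from IRB and sponsor reporting and from causality assessment, not loss from the record.

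The size cannot be estimated, because neither the expected AE rate nor the number of diagnoses that would be filed this way is given. The 6.7-point figure rests on 15 completers per arm and on the diverted event being that subject's only one. The Fisher results rest on assumed counts. The primary endpoint is untouched. The point concerns a listed secondary outcome and is worth correcting because the correction is cheap.

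**What to change.** Replace item d of section 5.8 with an onset-based rule, for example:

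> Any diagnosis with onset after informed consent is recorded on the AE log. Medical history is limited to conditions with onset before consent, including those first identified during the study; the evidence for onset before consent is noted in the source documents.

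Repeat the rule in the CRF instructions and cross-refer to it from 5.19.2.

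This does not remove all discretion. The PI still judges when a condition began and how it relates to study activities, and still knows the allocation when doing so. What changes is that the PI no longer decides whether a diagnosis with post-consent onset counts as an AE, and that each decision to file one as history leaves documented evidence a monitor can check.

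The cost is a short protocol and CRF change, a slightly longer AE log and a somewhat higher reported AE frequency in both arms.
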